A.2.2 *Laparoscopic Pyeloplasty (LP)* – This minimally invasive technique utilizes the same principles as OP, but is performed intracorporeally using trocars and laparoscopic instruments. Usually three or four separate, small incisions (~1 cm) are used. Long-term success rates have been shown to be identical to OP with similar costs; however, patients usually experience shorter hospitalization, but longer operative times.^{17,20,26-29} Patients are hospitalized typically for 1 day and discharged home with either an external catheter or internal ureteral stent as in OP. LP has failed to be widely adopted because of the high technical demand and steep learning curve, especially in pediatric patients who have decreased operative working space.

A.2.3 *Robotic-Assisted Laparoscopic Pyeloplasty (RALP)* – RALP is an extrapolation and advancement of LP, providing a solution to the technical demands and steep learning curve of LP.³⁰⁻³² RALP provides a 3D, magnified image, with increased instrument freedom and articulation. The surgeon sits at a console and his movements are transmitted to the intracorporeal robotic arms. Three or four small incisions are utilized to place the robotic arms, all less than 1.0 cm. Rather than placing the incision on the flank, as is done with OP, RALP incisions can be concealed in the umbilicus and on the lower abdomen. These patients are typically discharged the day after surgery with an internal ureteral stent. Robotic surgery has revolutionized the surgical landscape, offering the ability to perform increasingly complex operations through a minimally invasive approach without the significant learning curve associated with a pure laparoscopic surgical approach.³⁰⁻³³ In fact, recent data show decreased utilization of LP, as RALP becomes more common.^{1,34}

A.3. Standard of Care: Robotic vs. Open Pyeloplasty

In adults, a robotic approach has become the standard of care; however, in children a dichotomy exists. At some institutions, children as young as 6 months^{35,36} undergo a robotic procedure, while at other institutions, children as old as 18 years old still have open procedures.^{1,2,34} Few studies comparing pediatric RALP and OP clinical outcomes exist; none are randomized. However, the following has been shown:

- Current literature suggests long-term outcomes between RALP and OP are equivalent.⁸
- RALP patients require less pain medication compared with OP.^{8,37}

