- Nearly two-thirds of families would prefer robotic surgery scars.¹⁰
- Shorter mean hospitalization for RALP, typically by an entire day (2.3 vs. 3.5 days, respectively).⁸

No clear consensus exists as to whether robotic or open pyeloplasty should be the standard of care. The only way to resolve this issue is to conduct a randomized controlled trial in which outcomes that matter to both patients and surgeons are considered. However, two clear issues must be overcome in order to succeed. First,

we need to determine what measures and outcomes truly matter to patients, as well as physicians. Second, we need to insure that the many factors that have impeded prior RCTs of surgical procedures are overcome.

A.4 Patient-Centered Outcome Measures

Studies of surgical procedures have tended to focus on clinical outcomes (e.g., length of stay, pain control, complications). While these types of 'traditional measures' are clinically important to ensure safety and efficacy of surgical procedures,³⁸ they do not always take into account the perspective of the patient or family.

Research has demonstrated that patient experience and clinical quality/outcomes are distinct entities.³⁹ We believe that researchers must pay attention to patients' treatment experiences or patients' evaluations of their own outcomes. By focusing on these 'patient-centered outcomes,' we will be able to improve outcomes from surgical procedures in ways that are most important to patients and their families.²⁰

In the field of urology there has been sparse attention to patient- and family-centered outcomes in clinical trials. For example, studies of RALP have mostly used generic research instruments to assess preoperative and postoperative quality of life and scar perception after open and robotic pyeloplasty.^{10,40} While these studies provide useful data, they lack patient and family input into the creation of these research instruments and identification of outcomes that are meaningful to the patients and their families. In order to conduct an accurate, useful comparative effectiveness study aimed at determining which surgical modality is superior for treatment of pediatric UPJ obstruction, we must identify and collect data on patient/family-- outcomes.

A.5. Difficulties of Conducting Randomized Controlled Trials in Surgery

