C.2.2 Patient Identification and Recruitment. All participants will be recruited from the pediatric urology service at Riley Hospital for Children in Indianapolis, IN. We will identify pediatric patients with a UPJ obstruction requiring surgical intervention, using a double check system to avoid missing potential study subjects. Our clinical schedulers or surgeons in clinic will identify all potential study patients and flag them for the study PIs or RAs to review patient history. In addition, each week one of the study PIs ([name]) will assess all new patient referrals to identify any additional potential study candidates.

Once eligible patients are identified, they will be introduced to a member of the research team. Following the recruitment strategy developed in Aim 1, the study team member will introduce the study to the patient/family including presenting the expanded communication/ information pieces, the recruitment video and brochure, that were developed for the pilot study. If they agree, they will provide verbal consent and be shown the recruitment video. This strategy will include a general description of the different surgical modalities, as well as risks and benefits of each procedure. Emphasis will be placed on the fact that both options are equivalent. If they decide to be on the study, they will be consented in clinic, randomized to the study, and asked to complete a brief questionnaire as to why they decided to participate. During the enrollment process, the ICS and Assent (for the participant who is 7 years or older) will be reviewed verbally. Participants will be provided with a hard copy to read and time to ask questions. After signing the consent and assent, participants will be given a copy for their record.

If they decline they will be asked to complete a brief questionnaire as to why they decided not to participate.

[figure not shown]

Figure 2 shows the potential recruitment paths when an eligible patient is approached to participate in the study. The blue dotted line reflects those patients/families that agree to participate in the randomized pilot study. The study RA will obtain informed consent from these families utilizing the documents designed in Study Aim 1. The pink dotted line reflects those patients/parents who are NOT willing to participate in a randomized study. Following their decision NOT to participate in the randomized study, the study RA will ask these

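### C.2.2 has recruiters stress that robotic and open pyeloplasty are equivalent, without qualification; A.3 supports this only tentatively and only for long-term outcomes

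*Protocol*

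**What the plan says.** C.2.2 describes how an eligible family is approached. On the content of the message it says: "This strategy will include a general description of the different surgical modalities, as well as risks and benefits of each procedure". The next sentence sets the emphasis: "Emphasis will be placed on the fact that both options are equivalent". Families who accept are consented and randomised, and fill in a short questionnaire on why they joined. For the others: "If they decline they will be asked to complete a brief questionnaire as to why they decided not to participate".

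The evidence summary is in A.3. It opens with "Few studies comparing pediatric RALP and OP clinical outcomes exist; none are randomized" and then lists four findings that it presents as shown:

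- "Current literature suggests long-term outcomes between RALP and OP are equivalent"
- "RALP patients require less pain medication compared with OP"
- "Nearly two-thirds of families would prefer robotic surgery scars"
- "Shorter mean hospitalization for RALP, typically by an entire day (2.3 vs. 3.5 days, respectively"

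A.3 then concludes that the field has not settled on a standard of care and that a randomised trial is needed to settle it. The Specific Aims and C.2.7 leave superiority to a later, larger trial that this pilot is meant to help size. Sub Aim 2b makes the performance of the recruitment approach itself an object of study.

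**The concern.** Equipoise and equivalence are different claims. Equipoise says that it is not known which option is better. Equivalence says that the two are known to be the same. The trial is justified by the first, while C.2.2 tells recruiters to stress the second, as a fact and for outcomes in general.

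Two things are at stake. One is the accuracy of what families hear before they decide. The other is the use of the recruitment data. A.5 lists reasons why families refuse surgical trials. Among them are a preference for one procedure, and a parent's fear of feeling responsible if the treatments turn out unequal. A message of equivalence speaks directly to both. If acceptance and the stated reasons are gathered under that message, they may not describe what would happen in a larger trial whose information says plainly that the answer is unknown.

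**Working it through.** No design figure depends on this sentence, so there is nothing to reproduce. The check sets the instruction against the protocol's own evidence.

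**1. Scope.** C.2.2 covers both options with no outcome named. The A.3 bullet on equivalence covers long-term outcomes only. The statement in A.2.2 that long-term success is the same as with open surgery concerns conventional laparoscopic pyeloplasty, so it does not widen the support for the robotic operation.

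**2. Strength.** C.2.2 calls equivalence a fact. The A.3 bullet says the literature suggests it, and the sentence introducing the list says that studies are few and none is randomised. The bullet cites one source, a comparison of robotic pyeloplasty with a cohort of open operations. The protocol cites the same source for the shorter stay and, with a second reference, for the lower use of pain medication. The only cited support for equivalence is thus also cited for differences.

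**3. Direction of the other A.3 findings.** Two bullets report an outcome difference in favour of the robotic operation (pain medication and stay). One reports a preference (scars), which is not an outcome difference.

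**4. Overlap with what the pilot measures.** C.2.7 lists length of stay, pain medication use and scar perception among its outcomes. These are the topics of the three A.3 bullets in step 3. The unqualified wording therefore reaches outcomes that the protocol itself treats as open.

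**5. The one pair of numbers.** A.3 gives mean stays of 3.5 days (open) and 2.3 days (robotic): 3.5 − 2.3 = 1.2 days, which agrees with its description of about a day. This should not be taken as the expected effect here. A.2.1 puts open stays at 1 to 2 days, and A.2.3 says robotic patients usually leave the day after surgery. If that counts as a 1-day stay (an assumption), the gap is between 1 − 1 = 0 and 2 − 1 = 1 day. The figures show that equivalence on stay is not established. They do not show how large a difference this pilot would see.

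**6. Effect on acceptance.** The protocol gives no expected acceptance rate, no rate under any other message and no threshold for success beyond the goal of ten to twenty patients. No effect can be computed.

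**The case against.** The strongest reply is that the sentence should be read in context. The sentence before it promises the risks and benefits of each operation, so families are not simply told that the two are the same. Equivalent may have been meant as comparably acceptable, or as shorthand for long-term results. The consent and assent are also reviewed verbally, with a written copy and time for questions. C.1 commits the Aim 1 work to exploring what parents want to know without coercion or untruth.

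Much of this stands. C.2.2 does not strictly contradict itself, and a milder meaning is possible. But the milder meaning is not what is written, and equivalence is the element singled out for emphasis.

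A second reply is that the A.3 differences come from earlier non-randomised comparisons. In this pilot both arms receive the same type of stent, a standardised regional block and the same discharge plan (C.2.5, C.2.6), so those differences may shrink. That is fair, but it argues for uncertainty and not for stating equivalence as a fact.

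A third reply is that the pilot can detect the problem itself. Reasons are collected from those who accept and those who decline, decliners are invited to a session on their decision, and C.2.8 asks which parts of the strategy were compelling. This mitigates the concern. However, none of these steps names the equivalence message, and all families approached under the instruction would have heard it.

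A reader might go further and infer that families are actually misinformed, or that consent is defective. The documents do not support that, because the script, video, brochure and consent form are not shown and may be worded more carefully. A reader might also infer that acceptance is inflated. A.5 makes this plausible, but nothing in the protocol shows it.

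**Conclusion.** Wrong as written, of minor to moderate severity. The recruitment instruction states as a general fact something that the protocol's own evidence section supports only for long-term outcomes, only tentatively and without randomised data. The same section reports short-term differences and a scar preference on topics that the pilot measures.

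The consequence is limited to the accuracy of the recruitment message and to how far the Sub Aim 2b findings carry over to a later trial. No sample size, analysis or outcome definition changes. The size and direction of any effect on acceptance cannot be determined. The count of matching topics shows where the wording overreaches and does not measure harm. The conclusion rests on reading the sentence as written and assumes nothing about the unseen materials.

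**What to change.** Replace the sentence in C.2.2 with wording such as: *Recruiters will stress that limited non-randomised studies suggest similar long-term outcomes, that some short-term differences have been reported, and that it is not known which operation is better overall for children and families, which is why the study is being done.* This keeps the part that A.3 supports, mentions the reported differences and states the uncertainty that justifies randomisation.

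Then check the script, video, brochure and consent form, and edit them only if they carry the unqualified claim.

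The cost is one sentence, a read-through of the materials and IRB review of any edits. Acceptance of randomisation might be somewhat lower under the revised message. That is an assumption, since the protocol gives no figure.

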**Pediatric Robotic versus Open Pyeloplasty: A Pilot Randomized Control
Study**

[name]

Protocol ID 1403886306

ClinicalTrials.gov ID NCT04884945

Specific Aims

Technological innovations are an ongoing reality in clinical medicine, most dramatically in the operating room. Each advance is often heralded as an improvement in patient care, promising to correct deficiencies and advance standard operative procedures. Unfortunately, these new technologies often lack sufficient evidence to support such claims. Robotic assisted laparoscopic (RAL) surgery continues to gain popularity among pediatric surgical specialists, particularly for reconstructive procedures such as correction of ureteropelvic junction (UPJ) obstruction or vesicoureteral reflux (VUR).^{1,2} In these operations, where traditional open surgery yields a nearly 95% clinical success rate,³⁻⁶ it is difficult to demonstrate improvement with a new surgical technique. Despite these impressive outcomes with the open approach many pediatric urologists are shifting towards newer RAL approaches, claiming faster recovery⁷⁻⁹ and improved cosmesis¹⁰ with a nominal increase in surgical cost.¹¹ To date, no randomized controlled trials exist in the pediatric population comparing robotic to open surgery. However, this is not unusual. There is a striking dearth of comparative effectiveness research in pediatric surgical specialties, especially given the wide range of available therapies for a variety of surgical problems. Conducting randomized controlled trials of surgical interventions can be very difficult, especially in the pediatric population. One barrier frequently encountered is difficulty recruiting patients and families to participate in a randomized controlled trial (RCT) that involves surgical procedures.¹²⁻¹⁶ Patients and their families often reject RCTs, because they do not wish treatment to be decided by chance, the family is concerned that the doctor-patient relationship is affected by participation in a RCT, or the parent may have feelings of personal responsibility if the treatments are unequal.¹²⁻¹⁴ In order to use RCTs to determine treatment superiority, appropriate and meaningful outcomes must be identified and measured.

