families if they would be willing to 1) participate in a group session with the PEC team regarding their decision not to participate in the randomized study (See Figure 1, Session #5 and Figure 2) if they would be willing to allow our study team to collect data on the outcome measures being utilized for our study (See Section C.2.7). These families would not be randomized, but instead would be allowed to decide for themselves which procedure they would like to have performed. By utilizing this approach we are guaranteed to obtain useful data, even if we are unable to successfully implement a pilot randomized trial.

C.2.3 Compensation. Study participants will be compensated for their participation per findings from Aim 1. Aim 2, families who agree to participate in the randomized pilot study will receive a parking voucher during their child's hospitalization and subsequent follow-up appointments. They will receive \$25 dollars for the initial follow up visit at 2 weeks and \$10 for each follow-up visits (6 weeks, 3 months, 9 months) for a total of \$55 if they complete all the follow up visits.

C.2.4 Patient Randomization Procedure Once parent/guardians have signed informed consent, patients will be immediately randomized to either RALP or OP by using a pool of 20 cards of which 10 say "robotic surgery" and 10 say "open surgery." Each patient will then have a card randomly picked for them, thus ensuring an equivalent number of patients in each arm of the study. The attending surgeon for the patient will assist or perform the operation to maintain continuity of patient care.. A single robotic surgeon will be involved in all robotic procedures and one of four senior surgeons will be involved in any open procedure.

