C.2.5 Operative Intervention Each subject will have anesthetic induction and intubation. All patients will undergo a cystoscopy (endoscopy of the bladder) and retrograde pyelogram (instillation of contrast into ureter and across the UPJ) to confirm diagnosis of UPJ obstruction. An internal double j stent will be placed in the affected ureter (small, completely internal tube resting in the ureter held in place with curl in the kidney and bladder) and a bladder catheter placed. A standardized regional anesthetic block will be performed regardless of surgical approach. The pain service will place the block and follow the patient for pain management post operatively. Either RALP or OP will then be performed. Each patient will have standard anesthesia reversal and extubation.

Upon completion of the procedure, dressings will be placed on all surgical incisions, as well as anticipated locations of where incisions would be for the other procedure. Thus, all patients will have the same numbers of bandages (4) on all possible surgical sites, regardless of surgical approach.

C.2.6 Postoperative Care The patient will be transferred to the surgical floor once all standard PACU criteria have been met. All medication administration will be documented for postoperative pain. A clear liquid diet will be initiated, and diet will be advanced as tolerated. On postoperative day one (POD #1) the foley catheter will be removed and intravenous fluids will be stopped. All pain medication will be converted to an oral route with a plan for an early afternoon discharge if patient meets discharge criteria. Discharge criteria includes tolerating a regular diet, pain controlled on oral medication, ambulating without assistance and voiding spontaneously. Patients are followed at 1 week, 2 weeks, and 6 weeks post op. Their subsequent follow up appointments (3 months, 6 months, and 12months) are from the time of their prior visit. .

C.2.7 Measures. The patient-centered outcome measures that will be utilized in this study have been informed by the work of Aim 1. The list of outcomes below is not an exhaustive one, but does serve to outline that has been affirmed by the work in Aim 1.

Outcome Measure	Interval	How Obtained
Length of Hospital Stay (days)	Once, after discharge	Chart review by RA
Pain Medication Use (dose/freq)	Once, after discharge	Chart review by RA
Surgical complications	Once, after discharge	Chart review by RA, Clavian-Dindo classification ⁵²

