Total Hospital Charges and Estimated Costs	Once, after discharge and data deposited to PHIS database	PHIS database will be queried for charge and cost data submitted by the hospital
Pain Scores	Every 4 hours while hospitalized 1 and 2 week post op follow up	Chart review by RA (hospitalization and post op follow up)
Patient Experience: Side effects of medication and impact; Experience of having a temporary ureteral stent 4; Ease of removing stent; Return to activity; Financial burden reported by family	2 week post op follow up	REDCap survey or at time of 2 week post op follow up
Time until parental return to work	2 week post op follow up	REDCap survey or at time of 2 week post op follow up
Scar perception	At hospital discharge, and at 1,2, and 6 post op follow ups, and 3mo follow up scheduled at 6week follow up	REDCap survey or at time of post op follow ups, using the Patient Scar Assessment Questionnaire ⁵³ (PSAQ)
Quality of Life (post intervention)	At hospital discharge, at 1 2, and 6 week post op follow ups ,and 3 mo return visit scheduled at 6week follow up	REDCap survey or at time of post op follow ups, using the Glasgow Children's Benefit Inventory (GCBI)

Post op follow up refers to a follow up encounter in clinic or by phone. Type of encounter is determined by time interval and medical need

After completion of the pilot study, these outcomes will allow for an accurate power calculation, which will allow us to determine the number of patients needed for a large-scale study to determine superiority of either RALP or OP in the treatment of pediatric UPJ obstruction.

C.2.8 Validation of the Recruitment Strategy Patients/families that agree to either participate in the randomized pilot study or alternatively those who agree solely to the collection of outcomes data will be brought together by the PEC team in order to further refine the recruitment strategy that was developed in Aim 1 (See Figure 1). These two groups will attend separate sessions in order to better understand what components of the recruitment strategy were compelling and how the strategy can be improved.

C.3 Study Timeline

	YEAR 1				YEAR 2			
	Qtr 1	Qtr 2	Qtr 3	Qtr 4	Qtr 1	Qtr 2	Qtr 3	Qtr 4
Identification of Patient-Centered Outcomes								
Feasibility Study								
Data Analysis and Publication of Findings								
Writing of R01 Level Grant								

C.4 Potential Pitfalls

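### Parental return to work is asked only at 2 weeks, so any later return date is lost, although a 6-week contact already exists

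*Protocol*

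**What the plan says.** The outcome table in C.2.7 Measures includes "Time until parental return to work". Its interval is the 2-week follow-up, and the collection method is "REDCap survey or at time of 2 week post op follow up". No other row repeats the item, and no section says how to record a parent who is not yet back.

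The protocol already provides later contacts:

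- C.2.6 Postoperative Care: "Patients are followed at 1 week, 2 weeks, and 6 weeks post op", with further appointments after that.
- C.2.7, quality-of-life row: collected at discharge, "at 1 2, and 6 week post op follow ups" and at a 3-month visit, by REDCap survey or at the follow-up itself.
- C.2.7, note under the table: "Post op follow up refers to a follow up encounter in clinic or by phone".

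On use of the data, C.2.7 states that "these outcomes will allow for an accurate power calculation" for a large superiority trial. Under C.2.2, families who decline randomization may let the team "collect data on the outcome measures being utilized for our study", so the same schedule applies to them.

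**The concern.** The outcome is a duration, but the schedule can only measure durations that end within about 14 days. Anything longer is right-censored at the 2-week contact. How to analyse censored values can be left to an analysis plan. Whether the date is ever asked for is a data-collection decision, and the protocol makes it here.

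What is lost is the unrestricted mean, its standard deviation and the upper tail. These are the quantities a naive sample-size calculation would use, and the protocol presents the pilot data as the basis for such a calculation. The Specific Aims also describe surgeons as "shifting towards newer RAL approaches, claiming faster recovery". That is a general claim about robotic surgery and does not mention parents' work, but it makes a difference between arms on this outcome plausible. If the arms differ, the censored fraction would probably differ too.

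**Working it through.** The protocol gives no effect size, standard deviation, power or return-time distribution for this outcome, so there is no planned figure to reproduce. From the protocol come the 2-week (day 14) and 6-week (day 42) contacts, the enrollment goal of 10 to 20 patients, and the pool of 10 cards per arm (C.2.4). Everything else below is assumed, and the counts assume that every family has a parent with a job to return to.

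**Step 1. Bound without a distribution.** Suppose a share *p* of an arm is not back at day 14 and all are back by day 42. Each such time lies between 14 and 42 days, so the arm mean is undetermined over *p* × (42 − 14) = 28*p* days. The chance that at least one of *n* families is affected is 1 − (1 − *p*)^*n*.

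| *p* | width of arm mean (days) | at least one of 20 | at least one of 10 |
|---|---|---|---|
| 5% | 1.4 | 64% | 40% |
| 10% | 2.8 | 88% | 65% |
| 20% | 5.6 | 99% | 89% |

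**Step 2. Illustration with assumed exponential times.** For mean *m* and cut-off *c*:

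- P(T > *c*) = exp(−*c*/*m*)
- restricted mean = *m*(1 − exp(−*c*/*m*))
- variance of min(T, *c*) = 2*m*²[1 − exp(−*c*/*m*)(1 + *c*/*m*)] − (restricted mean)²
- N per arm (80% power, two-sided 5%) = 7.849 × (var₁ + var₂)/difference²

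| Assumed means | Cut-off | Restricted means | Difference (days) | N per arm |
|---|---|---|---|---|
| 4 vs 6 | day 14 | 3.88, 5.42 | 1.54 | 106 |
| 4 vs 6 | day 42 | 4.00, 5.99 | 1.99 | 102 |
| 4 vs 6 | none | 4, 6 | 2.00 | 102 |
| 8 vs 12 | day 14 | 6.61, 8.26 | 1.65 | 139 |
| 8 vs 12 | day 42 | 7.96, 11.64 | 3.68 | 101 |
| 8 vs 12 | none | 8, 12 | 4.00 | 102 |

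Worked entry, 8 vs 12 at day 14: the variances are 23.1 and 25.4, and 7.849 × (23.1 + 25.4)/1.65² ≈ 139 (unrounded inputs).

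Not back at day 14: 3.0% and 9.7% for means 4 and 6, or 10 × (0.030 + 0.097) ≈ 1.3 of 20 families. For means 8 and 12 it is 17.4% and 31.1%, or about 4.9 of 20. The medians, *m* ln 2, are 2.8, 4.2, 5.5 and 8.3 days, all inside the window.

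**Step 3. What the 14-day data leave open.** In the 8 vs 12 case, let the mean residual time after day 14 be *r* in both arms. The unrestricted difference is 1.65 + *r* × (0.311 − 0.174). For *r* from 0 to 28 days this runs from 1.65 to 5.51 days (unrounded inputs), and the 14-day data cannot narrow that range.

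**Step 4. A different assumption, and a different direction.** Take lognormal times with median 7 days and log-SD 0.5, and size a trial for a fixed 2-day difference. Then 8.3% return after day 14. The SD is 4.23 days with all dates known, 3.31 if late times are set to 14, and 2.82 if late families are dropped. N per arm is 71, 44 and 32. Over assumed medians of 5 to 10 days and log-SD of 0.5 or 0.8, 2% to 34% return after day 14 but at most 3.7% after day 42. Under these assumptions a 6-week question would recover nearly all the missing dates.

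**Step 5. Pilot noise.** With 20 patients (18 degrees of freedom) and normal data, the 95% interval for a variance is 18/χ²₀.₉₇₅ = 0.57 to 18/χ²₀.₀₂₅ = 2.19 times the estimate. With exponential times (8 vs 12, 10 per arm), simulation puts the pooled variance estimate between about 0.24 and 2.8 times the truth. Both ranges are wider than the change from 102 to 139.

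**The case against.** A 2-week horizon is a defensible choice. Stays are short, discharge is planned for the day after surgery if criteria are met, and asking early limits recall error. Several useful summaries survive the cut-off. No aim of this feasibility pilot depends on parental return to work, and the power-calculation sentence covers the whole outcome list. The size of the loss rests on assumed distributions. One illustration shows a negligible effect, and the larger one lies within pilot noise. Even the direction is unsettled: restricting to 14 days raises N in Step 2, while capping or dropping late times lowers it in Step 4. Finally, C.2.7 calls its outcome list non-exhaustive, and the survey wording is not shown.

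Most of this stands and limits the weight of the point. It does not remove it. A non-exhaustive list leaves room for further outcomes but does not change the interval stated for this one. The choice between REDCap and the visit concerns mode, not a later time. A survey could ask for an expected return date, but that is not an observed one. The uncertainty about the distribution is itself something a pilot can help reduce, and the present schedule hides the part beyond day 14.

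**Conclusion.** The point holds as a minor design improvement. The protocol fixes one collection time for a duration and provides no way to learn a return date after about day 14. An analysis plan cannot repair that.

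The consequence is unknown and possibly small: nothing if every parent is back within 2 weeks, and up to 28*p* days of uncertainty in an arm's mean if a share *p* is not and all are back by day 42. It matters only if the unrestricted mean, its SD or the upper tail is used, and the protocol does not say that the large trial will be powered on this outcome. The N figures are illustrations under assumed distributions, not predictions.

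**What to change.** Add one conditional item to the existing 6-week survey or phone contact: parents who were not back at work at 2 weeks give the date of return, and those still not back are censored at that contact. Apply the same to return to activity (the patient-experience row) only if that item is recorded as a time. Use the same item for families who decline randomization but allow data collection.

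The cost is one extra question (two if return to activity is a time) for some families only, about 1 to 5 of 20 in the exponential illustrations, with no new visit or staff. Dates asked at 6 weeks carry up to about four weeks of recall, and some 6-week contacts may be missed.

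If the 2-week schedule is kept, report the share back by 2 weeks or the 14-day restricted mean, not an unrestricted mean.
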